Expected Outcomes Based on geography and shortage of pediatric palliative subspecialists in Nebraska, the current model of hospice services is one in which pediatric patients are managed by local adult-based hospice teams after discharge from the pediatric hospital (34 such in the past 16 months). Sixty percent of academic pediatricians in Nebraska who served as primary providers for consecutive pediatric home discharge patients self-reported feeling “very deficient” to “deficient” when asked about competence after supporting terminal patients and families in care at home (n=12).¹ The knowledge gap and discomfort in managing children with complex symptom burden is magnified further for family practice or internal medicine teams serving in hospice roles for children in rural communities. Through a new telepalliative technology platform, this study fosters collaboration and communication to improve the quality of care for pediatric patients receiving hospice care in rural states. This model implements human interaction through technology to challenge the existing paradigm of silo-based care of pediatric palliative care patients. With roll-out of this intervention, we anticipate increase in pediatric hospice utilization (decreased in-hospital deaths). If feasible this model could transform the pediatric hospice care delivery in the state of Nebraska with expanded opportunity for application in settings with similar subspecialty provider shortages.

Table 1. Aims, Measures, and Time Points for this Exploratory Pilot Feasibility Study		
Aim	Completed by	Measures and Designated Timepoints
Investigate symptom burden for pediatric patients and the quality of life impact for pediatric patients and their families	Patient Parent	PROMIS-37 – Every 15 days, as child is able Proxy-PROMIS-37 and PedsQL Family Impact completed by Proxy – Every 15 days
Evaluate the self-efficacy (comfort), knowledge, and self-perceived adequacy of local hospice providers	Hospice Nurse Team	Pediatric Palliative Care Questionnaire – Enrollment and end of study Qualitative Debriefing Survey (2 qualitative questions) – End of study
Explore the acceptability of teleconferencing services as a form of pediatric palliative care consultation	Hospice Nurse Team	Technology Acceptance Model (TAM) Tool – After telehealth encounters

Research Plan

Background and Significance

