Study Variables and Measures – Although there is an increasing call for pediatric providers to foster patient voice, pediatric care teams often grade symptoms and report quality of life or the parent reports as proxy. The graded symptoms which lead to patient-interpretation of quality of life often include subjective symptoms such as nausea, dyspnea, fatigue, insomnia, anxiety, depression, mental clarity, and pain. This project thus commits to triangulate the lens on lived experience by eliciting child, parent, and family perspectives on symptoms and on quality of life. **Symptom and quality of life** outcomes will be obtained from a triad-view: from the child perspective (using the PROMIS-37™), from the guardian and hospice nurse perspective on the child's experience (using the PROMIS-37 Proxy Edition™), and from collective family perspective on family quality of life (using the PedsQL™ Family Impact Module).⁴⁴ Internal consistency reliability for the Total Scale Score (alpha = 0.88 child, 0.90 parent report).⁴⁵ Specific to pediatric illness, these scales have been utilized and validated.^{46,47,48,49,50,51} **Technology Acceptance** will be measured by the Technology Acceptance Model (TAM) questionnaire as has been used in adult telehealth hospice settings,^{52,53,54} consists of two six-item scales with reliabilities of 0.89 for usefulness and 0.87 for ease of use.⁵⁵ **Local hospice team sense of self-efficacy (comfort), knowledge, and self-perceived adequacy** of caring for pediatric patients will be measured using the Pediatric Palliative Care Questionnaire (known validity coefficients 0.88 and 0.92) and two qualitative interview questions asked pre- and post- intervention.⁵⁶

Step-by-step outline of the CALLING protocol – With a letter of agreement between the pediatric palliative care team and the local hospice providers the teams will use the web-conferencing platform recommended by the American Telemedicine Association. The two teams can connect virtually, and even include the pediatric patient and family.

- **Baseline Needs Assessment to Guide Care is current standard of care** – Collaborative completion of baseline demographics and needs assessment form covering financial, psychosocial, demographic domains and goals of care to include advance care planning will be completed at first visit with patient, family, local hospice team to direct longitudinal care approach.⁵⁷ This is current standard of care (not new to hospice research project).

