- **Consent/Enrollment** - Consent and enrollment procedures will follow strict Institutional Review Board expectations and ethical standard.
- **Stakeholder Survey** – Local hospice team will be asked about their perceived self-efficacy (comfort), knowledge, and perceived adequacy in caring for pediatric children in using quantified Pediatric Palliative Care Questionnaire scale pre- and post-child enrollment.

- *Symptom Burden and Quality of Life* – Child, guardian, and hospice team nurse will complete Pediatric PROMIS-37™ every 15 days to assess for symptom burden and translated quality of life.
- *Interdisciplinary (IDT) Telepalliative Care Meetings* –Technology Acceptance Model survey will occur every 15 days (in the pediatric palliative educational arm and in the patient-specific case discussion arm) as an automatic screen on the closing telepalliative screen to evaluate acceptability of technology interface. The reason for this frequency is that Medicaid requires that hospice interdisciplinary team interactions occur at a minimum of every 15 days.
- *Team Debriefing* – At enrollment and at the conclusion of the study period (six months per enrollee with total project duration 2 years) or within 3 days following a child’s natural end of life; the local hospice team members will be invited to engage in a qualitative interview with two thematic topics: 1. Please describe your experience caring for a pediatric patient and 2. Please describe your experience with telepalliative use. This interview will be recorded and coded for content using Atlas.ti software.

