Data Plan – Descriptive statistics will be computed for each outcome variable at each time point. Repeated measures ANOVA and trend plots will be used to explore quantified symptom burden and quality of life trends over time. The association between individual and multiple symptoms will be explored via linear and multiple linear regression. Bland-Altman plots will be used to assess concordance between symptom and quality of life reporting. Crude (unadjusted) associations between demographics (such as family economics, diagnosis, level of technology, delay to initial palliative care) and symptoms / quality of life will be explored via ANOVA or linear regression, as appropriate. A similar analysis will be used to explore the association between how hospice team self-perceived confidence and knowledge of pediatric palliative care and child symptom and quality of life. In the event the assumptions of the parametric tests identified above are violated, the appropriate non-parametric test will be used. When a non-parametric test is used, the median and interquartile range for continuous outcomes will be reported. A significance level of 0.05 will be used to judge statistical significance. In addition to monitoring for statistical significance, the study team will follow minimally clinically important

difference (MCID) for symptom burden or quality of life values over time.⁵⁸ MCID has been defined as “the smallest difference in a score of a domain of interest that patients perceive to be beneficial and that would mandate, in the absence of troublesome side effects and excessive costs, a change in the patient's management.”⁵⁹ Content of the two qualitative interview questions will be analyzed thematically using a qualitative coding methodology in Atlas.ti ([name] has completed graduate level qualitative coursework >9 credit hours and published >4 qualitative method manuscripts).⁶⁰

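### TAM scores exist only for telehealth sessions that reach the closing screen, and stopping telehealth triggers no survey, debrief or count, so Aim 3 means may overstate acceptability

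*Combined protocol and SAP*

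**What the plan says.** Aim 3 is about the acceptability of teleconferencing, and the Project Abstract also names acceptability in the study objective. Table 1 gives one measure for this aim: "Technology Acceptance Model (TAM) Tool – After telehealth encounters". According to Study Variables and Measures, the instrument "consists of two six-item scales with reliabilities of 0.89 for usefulness and 0.87 for ease of use". The response range is not given.

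Delivery is described in the step-by-step outline, under Interdisciplinary (IDT) Telepalliative Care Meetings. The schedule is "Technology Acceptance Model survey will occur every 15 days (in the pediatric palliative educational arm and in the patient-specific case discussion arm", and in the same sentence the form is delivered "as an automatic screen on the closing telepalliative screen to evaluate acceptability of technology interface".

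Staff are also interviewed. The Team Debriefing item sets this "At enrollment and at the conclusion of the study period (six months per enrollee with total project duration 2 years", or within 3 days of a child's death, and says "the local hospice team members will be invited to engage in a qualitative interview with two thematic topics". One topic is caring for a pediatric patient and the other is experience with telepalliative use. Study Variables and Measures describes "two qualitative interview questions asked pre- and post- intervention". Table 1 lists the debriefing at end of study only and places it in the Aim 2 row.

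For analysis, the Data Plan has one general statement that covers the TAM: "Descriptive statistics will be computed for each outcome variable at each time point". It assigns repeated measures ANOVA and trend plots to symptom burden and quality of life, not to the TAM. The documents contain no rule for missing TAM forms, no count of sessions held against sessions due, no record of reasons for non-use, no survey prompted by stopping and no acceptability threshold.

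**The concern.** The form depends on use of the thing it evaluates. Its two scales measure usefulness and ease of use, and a low opinion on either is a plausible reason to decline sessions or stop connecting. The capture rule can therefore select on the construct being measured, and the plan collects nothing systematic that would show whether it had.

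The TAM is the only quantitative evidence for Aim 3, and the protocol looks ahead to statewide use and expansion elsewhere if the model proves feasible. In a pilot, a team that tries telehealth and gives it up is among the most informative observations on acceptability. The form is collected in both arms, so unequal stopping could also distort any comparison of acceptability between educational modules and case discussion.

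**Working it through.** **Step 1. What each situation yields under the text as written.**

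| Situation | TAM form | Interview |
|---|---|---|
| Session held and closed normally | Yes | Not affected |
| Session declined or missed | None | None prompted |
| Call lost before its close | None if the closing screen is not reached; the documents do not say what a dropped call displays | None prompted |
| Team stops while the child is alive and enrolled | None from then on; earlier forms stay in the data | None at the time of stopping; invitation at the end of the study period or within 3 days of a death |
| Child dies | No further sessions for that child | Invitation within 3 days |

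The enrollment interview cannot record a later decision to stop.

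**Step 2. Inputs.** The plan states no TAM mean, stopping rate or target, so there is no figure to reproduce. From the documents: one session per 15 days for at most six months. Taking six months as 180 days, 180/15 = 12 sessions at most per enrollee. Assumed: *q*, the share of teams that stop; *g*, the score gap between continuing and stopping teams; *k*, the number of sessions before stopping; an item score on a 1–7 scale; and stable opinions within each team.

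**Step 3. Late-session mean.** Let continuing teams average *C*. The mean over all teams is *C* − *qg*. After the others have stopped, the observed mean is *C*. Bias = *qg*.

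- *q* = 10%, *g* = 0.5: 0.10 × 0.5 = +0.05
- *q* = 20%, *g* = 1: 0.20 × 1 = +0.20
- *q* = 30%, *g* = 1: 0.30 × 1 = +0.30
- *q* = 50%, *g* = 2: 0.50 × 2 = +1.0
- *g* = 0: zero for any *q*

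**Step 4. Mean over all forms.** Stopping teams supply a fraction *w* = *qk* / (*qk* + 12(1 − *q*)) of the forms, and bias = *g*(*q* − *w*). With *g* = 1:

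- *q* = 30%, *k* = 1: *w* = 0.3/8.7 = 3.4%; bias +0.27
- *q* = 30%, *k* = 3: *w* = 0.9/9.3 = 9.7%; bias +0.20
- *q* = 20%, *k* = 6: *w* = 1.2/10.8 = 11.1%; bias +0.09

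**Step 5. A severe example.** Of 10 teams, seven score 6 throughout, and three score 3 and stop after one session. Session 1 mean: (7 × 6 + 3 × 3)/10 = 5.1. Every later mean: 6.0. Mean over all forms: (84 × 6 + 3 × 3)/87 = 513/87 = 5.90. No team has changed its view.

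**Step 6. Does the reason for stopping matter?** A simulation used 12 sessions, team means centred on 5.0 (SD 1) and session noise of SD 0.5. When low scorers were likelier to stop, the mean was 5.54 at session 12 and 5.26 over all forms. When stopping was unrelated to score, the figures were 4.99 and 5.0. In both cases 42% of teams were still connecting at session 12, so the amount of attrition alone does not reveal bias.

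**The case against.** A reader might infer three stronger things, and the documents support none of them.

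- *Staff are debriefed only at six months or after a death.* The Team Debriefing item also has an enrollment interview, and Study Variables and Measures says before and after the intervention.
- *Teams that stop vanish from the result.* Their earlier TAM forms remain. The closing interview is open to local hospice team members whether or not they still use telehealth, and it asks about that use. In a mixed-methods pilot this is relevant evidence.
- *Acceptance is overstated and TAM means will rise.* The documents give no stopping rate and no link between stopping and score. Sessions also end because children die, which is expected in hospice and need not bias the score.

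It is also fair to say that Aim 3 is exploratory, no trend test or decision rule rests on the TAM, and a by-session table that reported the number responding would show the fall in respondents. The example in Step 5 is severe: it assumes 30% stopping after one session, a 3-point gap and a full 12 sessions, when six months is a maximum.

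These points narrow the concern but do not remove it. The closing interview is qualitative and by invitation, may come months after a team stopped, and sits under Aim 2 in Table 1. It cannot correct a TAM mean. A falling number of respondents shows that people left, not why.

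**Conclusion.** The concern holds as a conditional risk. The only listed Aim 3 measure is observed only when a session reaches its closing screen. Stopping telehealth during enrollment prompts no measurement, and uptake is not counted. If stopping is related to low acceptance, later-session and pooled TAM means are biased upward. Over modest assumptions the late-session bias runs from +0.05 to +0.30 points, with larger values only under heavier stopping or wider gaps. If stopping is unrelated to score, the bias is zero.

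The stopping shares, score gaps and scale are all assumptions, so the figures show direction and range, not this trial's bias. The gap does not invalidate the pilot. It leaves the quantitative Aim 3 result unable to separate acceptance from attrition, and it is worth closing because the remedy is small. Separately, the three accounts of debrief timing do not agree.

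**What to change.** 1. Keep the closing-screen form.
2. When a team or staff member who has used telehealth stops, send one final TAM outside the platform, offer the existing two-question debrief, and record the reason for stopping.
3. Report sessions held over sessions due by team and arm, the number who stopped, and each respondent's last TAM score, alongside the by-session means with n.
4. Reconcile the debrief timing across Table 1, Study Variables and Measures, and Team Debriefing.

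Sending the TAM after every unattended meeting is not recommended: a usefulness and ease-of-use form has unclear meaning for a session the respondent did not join.

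The cost is a short protocol edit, a link to an existing 12-item form, one added trigger for an existing interview and a simple session log. The downsides are a few extra reminders to staff and a possibly less favourable acceptability figure.

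### The Data Plan names repeated measures ANOVA for the 15-day trends without its form or a rule for deaths and missed forms; a complete-case version would waste data, and visit means compare changing groups of children.

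*Combined protocol and SAP*

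**What the plan says.** The Data Plan section of the combined protocol and SAP is the whole quantitative plan. For the Aim 1 trends it states: "Repeated measures ANOVA and trend plots will be used to explore quantified symptom burden and quality of life trends over time". It adds that "Descriptive statistics will be computed for each outcome variable at each time point". If parametric assumptions fail, "the appropriate non-parametric test will be used", with no test named. The significance level is 0.05. The plan also says: "In addition to monitoring for statistical significance, the study team will follow minimally clinically important" differences over time.

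No sentence gives the form of the ANOVA, the occasions that enter it, or how a missed form or a death is handled. The plan does not say whether the trend plots show means or individual children.

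Other sections lead one to expect incomplete series:

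- The sample is children enrolling on home hospice, followed for at most six months (Sample and inclusion criteria; Selection methods and sample size).
- The Team Debriefing step sets an interview at the end of the study period "or within 3 days following a child’s natural end of life".
- Table 1 makes the child's own form conditional on the child's ability to complete it. The parent forms carry no such condition.

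There are several reporters. "Child, guardian, and hospice team nurse will complete Pediatric" PROMIS-37 forms every 15 days, and Study Variables and Measures says that symptom and quality-of-life "outcomes will be obtained from a triad-view".

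**The concern.** Classical repeated measures ANOVA needs a full row for each child, so one missed form, or death before the last occasion, removes everything that child contributed. In a hospice sample of 10 to 20 this could discard much of the Aim 1 data. The unnamed fallback would not help if it is a Friedman-type test, which also needs complete series. In any case it is triggered by failed assumptions, not by missing data.

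A different problem affects the summaries at each time point. They use whoever has a form at that visit. If sicker children die sooner, later means come from less burdened children and can drift in the direction the central hypothesis predicts, with no child having improved.

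At stake are avoidable loss of data from dying children and a possible misreading of the visit means.

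**Working it through.** The plan has no figure of its own to reproduce: the sample size is explicitly not power-based, and no death, completion or variance figure is given.

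**Inputs from the documents.** The interval is 15 days and the maximum follow-up is six months, taken as 180 days, so occasions = 180/15 + 1 = 13. The Project Abstract gives 10-20 children. Selection methods gives 10-20 per hospice. Counts of children scale with the total, but shares of forms do not.

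**Assumptions.** S is the proportion alive at day 180, with constant hazard. c is the completion probability of each form while alive. Misses are either independent or clustered within child or family (beta-binomial, ICC 0.3).

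**Share of forms used by a complete-case ANOVA**

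- Probability that a surviving child has all 13 forms, p: independent, c^13; clustered, the product over j = 0..12 of (a+j)/(a+b+j), with a = c(0.7/0.3) and b = (1-c)(0.7/0.3).
- Fraction of children complete: f = S × p.
- Share of collected forms used: 13f / (cD), where D is the sum over k = 0..12 of S^(k/12). D = 8.99 at S = 0.45 and 10.94 at S = 0.70.
- Probability of fewer than 2 complete children: (1-f)^n + nf(1-f)^(n-1).

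Example: S = 0.45, c = 0.90, independent. p = 0.9^13 = 0.254 and f = 0.45 × 0.254 = 0.114. Share = 13 × 0.114 / (0.9 × 8.99) = 0.18. With n = 10, the chance of fewer than 2 complete children is 0.68.

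| Completion | p | Share used, 45% alive | Share used, 70% alive | Fewer than 2 complete, 45% alive, n = 10 / 20 |
|---|---|---|---|---|
| 90%, independent | 0.254 | 18% | 24% | 68% / 32% |
| 95%, independent | 0.513 | 35% | 45% | 29% / 4% |
| 90%, clustered | 0.607 | 44% | 56% | 20% / 1% |
| 95%, clustered | 0.782 | 54% | 69% | 8% / under 1% |
| 98%, independent | 0.769 | 51% | 65% | 9% / under 1% |

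Completion and clustering matter as much as survival. With no missed forms at all, deaths alone leave 69% of forms in use at S = 0.5 and 83% at S = 0.7.

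**Precision.** These are simulated SDs of the estimated day-180 change, in score-SD units, complete-case against mixed model, n = 20.

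- About 45% alive: 0.33 against 0.19 (90% independent), 0.26 against 0.18 (90% clustered), 0.22 against 0.17 (98%).
- 86% alive and 98% completion: 0.15 against 0.14.

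The complete-case SD uses only simulated studies with at least 2 complete children. In the first case this leaves out 33% of studies at n = 20 and 68% at n = 10, so that comparison is not like for like.

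A separate calculation of the standard error of the mean slope (n = 20; intercept SD 8, residual SD 5, slope SD 0 to 1 per visit) gives complete-case to all-data ratios of 1.05-1.09 for deaths only at S = 0.7, and 1.39-1.50 when 5% missed forms are added. Missed forms drive most of the loss.

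**Bias of the test.** If exit depends on the current score (hazard ×1.0 to ×2.7 per SD) and the true change is 0, the complete-case change is 0.00 to +0.02. If exit depends on a child's own slope (slope SD 0.6, true change +0.30, 49-51% alive, hazards ×1.5, ×2.0, ×2.7), complete-case gives +0.15, +0.04, -0.03 and the mixed model gives +0.17, +0.12, +0.04. Neither is protected.

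**Visit means.** 300,000 simulated children, true change zero, within-child ICC 0.6, 15-day death probability 1 - exp(-h × exp(b × score)), higher score meaning more burden.

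- h = 0.06, 42-47% alive: means fall about 0.18, 0.30 and 0.41 SD for hazards ×1.5, ×2.0 and ×2.7 per SD of burden.
- h = 0.01, 83-88% alive: about 0.03 to 0.10 SD.
- b = 0 (death unrelated to burden): no fall.

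**The case against.** The strongest reply is that the Data Plan never says complete-case. Repeated measures ANOVA is sometimes fitted as a mixed model on all observed forms, and nothing says that all 13 occasions enter. Every rate above is assumed, and the results run from a small loss to a severe one with nothing in the documents to place the study. This stands, and it is why the point is conditional. It does not remove the need to state the form.

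Second, the clearest evidence of missed forms covers one instrument. The ability condition in Table 1 applies only to the child's PROMIS-37, so the loss may be smaller for guardian, nurse and Family Impact forms. This also stands.

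Third, the MCID definition quoted in the Data Plan is worded in terms of what patients perceive and of the patient's management, which points to within-child change. That is fair, but the plan does not say that the MCID will be applied that way rather than to visit means.

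Fourth, Table 1 calls this an exploratory pilot feasibility study, the analysis is to explore trends, and the sample size is not based on power. This limits the severity. It does not make discarding series reasonable when every child counts.

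Finally, a mixed model has limits of its own, given under the fix.

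**Conclusion.** The point holds in conditional form. The Data Plan names a method whose classical version fits badly with up to 13 assessments in hospice children, and it gives no rule for deaths or missed forms. If run complete-case, the test loses mainly precision. The amount depends jointly on survival, completion and clustering of misses, all of them assumed here. Too few complete children to run the test is a material risk mainly at n = 10, with about 5-10% independent misses or with half or fewer alive. The drift in visit means is a separate issue and needs death to be related to burden.

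A reader might infer two stronger things. One is that the trend test will use only a minority of the data whenever survival is moderate. The documents do not support this: at 70% alive three of the five cases above use more than half of the forms, and even at 45% alive two do. The other is that the ANOVA itself is biased toward improvement, or that a wrong confirmatory conclusion would follow. A complete-case test follows the same children and is close to unbiased for their change when exit depends on symptom level. It is biased if exit depends on a child's own slope, but so is the mixed model, and no decision rule rests on the test.

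Severity is minor to moderate: a cheap improvement worth making before analysis.

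**What to change.** In the Data Plan, for each reporter's score (child, guardian, nurse, and Family Impact), replace repeated measures ANOVA with a linear mixed model on all available assessments: random child intercept, time continuous or in a few windows, REML with small-sample degrees of freedom, and child-level jackknife standard errors. The jackknife matters because 15-day scores may be serially correlated. In simulation, model-based 95% intervals covered 94-95% with independent errors, 71-72% with autocorrelation 0.7 and 87-88% with child slopes (SD 0.5). Child-jackknife intervals covered 93-94% in all three.

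Show individual trajectories and within-child change beside the visit means, with the number alive and the number contributing at each visit. Say that the MCID applies to within-child change, and that trends describe children while alive.

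The cost is SAP wording only: the same forms and standard software. The downsides should be stated in the plan. The model assumes that missingness depends on observed scores. It does not resolve truncation by death or exit that depends on a child's slope. It also stays imprecise: with about half alive, the SD of the day-180 change is 0.25-0.29 score SD at n = 10 and 0.18-0.19 at n = 20. How to compare the educational and case-discussion arms over time is a separate question and is not part of this change.
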